## 10. HEALTH ECONOMICS

ALS is a devastating neurological disease for which there is no cure. The disease results in a progressive impairment in activities of daily living, including walking, eating and speaking. As a result, there is a significant negative impact on the quality of life of both patients and their families with associated considerable economic burden.

Expenses associated with the disease can be divided into direct and indirect costs. Direct costs are those expenses requiring payment, whether by the patient, government or a third-party payer (i.e., health insurance and non-profit-organizations), such as those associated with formal health care, medications, equipment, home or vehicle adaptations, medical devices, mobility aids and services. Direct costs can be further divided into healthcare costs and non-healthcare costs. Indirect costs represent opportunity loss, most notably lost income due to a patient's illness related absence from work or the voluntary caregiver duties taken on by family or friends. Both direct and indirect costs can overwhelm the financial resources of patients and their families and should be considered when evaluating the overall economic burden of ALS.

In this study, an exploratory cost-utility analysis for treatment with FAB122 will be conducted using the following data:

- Cost questionnaire: Data provided by a specific questionnaire for the direct and indirect costs associated with the disease (see annex 2). The consented patients will complete the questionnaire at baseline and every 3 months thereafter, up to the end of the study.
- eCRF: Some data will be gathered from the patient's dataset such as hospitalizations, concomitant medications, and occurrence of AEs.

The following cost parameters will be considered for the cost-utility analysis:

1. Number of visits classified per specialist and type of visit (scheduled vs not scheduled).
2. Number of hospitalizations related to ALS classified per unit of stay and length of stay.
3. Medication and administration cost (inpatient vs outpatient).
4. Specialized equipment / Devices cost (i.e. mechanical ventilation-invasive or not, artificial nutrition – percutaneous endoscopic gastrostomy).
5. Number of new orthopaedic devices (i.e. wheelchair).
6. Paramedical treatment visits (i.e. physical therapy, rehabilitation, occupational therapist, speech and language therapist, or otherwise specified by the patient).
7. Formal care (i.e. health professional) and informal care (i.e. familiar/friend).
8. Employment situation.
9. Occurrence of AEs.

An ad-hoc cost questionnaire will be completed at Baseline and every 3 months thereafter.

After the end of the study, analysis of each category will be done, then costs will be calculated by category and for all categories per patient. Costs would be calculated

according to local tariffs and according to guidelines for cost analysis in healthcare research. All costs will be presented in euros.

## 11. STATISTICS

### 11.1. Statistical Analysis Plan (SAP)

The statistical analysis will be carried out in accordance with the principles specified in the International Conference on Harmonization (ICH) Topic E9. A detailed Statistical Analysis Plan (SAP) will be made available before the un-blinding of the data base.

### 11.2. Sample Size Determination

No formal size calculation has been done for the extension study.

The main study plans to include approximately 300 patients. It is anticipated that 200-225 patients might be included in this extension study.

All subjects who completed the full study period in the main ADORE study and providing informed consent to comply with extension trial procedures are eligible to participate in this extension study.

### 11.3. Description of Statistical Methods

#### 11.3.1. Analysis Populations

Safety Analysis Set: The safety analysis set will consist of all subjects who receive at least 1 dose of IMP in the extension study.

#### 11.3.2. Demographics, baseline characteristics

Demographics and medical history will be retrieved from the main ADORE study.

#### 11.3.3. Subject Disposition

Subject disposition (analysis population allocation, entered, discontinued, along with primary reason for discontinuation) will be summarized using frequency and percent.

#### 11.3.4. Efficacy Analysis

Descriptive statistics (median, and the 25th and 75th percentiles with 95% confidence intervals) and Kaplan-Meier curves will be provided for patients participating in the extension study and patients that consented to only follow their vital status.

The primary aim of the analysis is to evaluate the difference between patients originally randomized to FAB122 versus those originally randomized to placebo using the extended follow-up data from the open-label phase. The difference in overall survival between patients originally randomized to FAB122 versus those originally randomized to placebo will be evaluated using a log-rank test, stratified for randomization factors. The effect of treatment will be expressed as hazard ratio. In case of non-proportional hazards, we will estimate the difference in restricted mean survival time (RMST).

---

In addition, we will explore the effect of treatment switching in the placebo arm using a rank preserving structural failure time model (RPSFTM) and inverse probability of censoring weights (IPCW). Details of the analyses will be provided in the SAP.

Changes in the in ALSFRS-R score, SVC, ALSAQ-40, EQ-5D-5L, and VAS score over time will be presented descriptively.

### **11.3.5. Safety Analysis**

Safety evaluations will be based on the incidence, severity, and type of AEs and clinically significant changes in the subject's physical examination findings, vital signs, and clinical laboratory results. Safety variables will be tabulated and presented for all subjects in the Safety Population. Data will be summarized by treatment and time. Exposure to study drug and reasons for discontinuation of study drug will be tabulated.

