#### 3.1.2 Safety Analysis Set Extension (SAFe)

The SAFe population includes all patients enrolled in ADOREXT who have received at least one dose of the investigational drug during the extension study, irrespective of satisfying other criteria. This population will be used for the analysis of safety and tolerability, and statistical analysis will be done “as treated”. Although all patients will be treated with FAB122 in ADOREXT, data will be presented also using the randomization groups of ADORE study.

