### 5 STATISTICAL ANALYSIS

#### 5.1 General considerations

Appropriate rounding will be performed for the summary statistics: arithmetic mean, median, SD (standard deviation) and confidence limits will be presented with one more decimal than the original data; minimum and maximum values will be presented with the same precision as the original data. In frequency tables, percentages will be presented with 1 decimal. P-values will be presented with 3 decimals, and those smaller than 0.001 will be replaced by <0.001.

Descriptive statistics presented in general summary tables will be the number of non-missing observations (n), mean, SD, minimum, median and maximum for quantitative data. For categorical data, frequency counts and percentages will be determined. The denominator when calculating percentages will be the number of patients in the applicable analysis population. Descriptive statistics will be displayed for all visits that a measurement is collected on, even if the endpoint is only referring to limited visits for the analysis.

Baseline is defined as the last value measured prior to first study treatment administration in ADOREXT study, unless otherwise specified. Typically, baseline data are collected at Visit 6 or 8 of the ADORE study. In case this value is missing for a specific patient in ADOREXT CRF data, but an earlier measurement is collected in ADORE study data, this value will be used as baseline instead. Unscheduled measurements are excluded as baseline value.

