#### **5.4.3 Disposition**

To present disposition, summaries will be provided for all randomized, enrolled in extension, treated in extension, and completed extensions along with reasons for early discontinuation. Completion status will be derived from CRF form “Study Completion”. Additionally, the number/percentage of patients in the mITT and SAFe will be presented. The patient disposition will be presented per treatment group and overall.

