### **5.6.1 Adverse events**

A treatment emergent adverse event (TEAE) is defined as an adverse event that appears at or after first dosing of extension. In case of (partially) missing start/stop dates, refer to Section [5.2](#).

An AE overview table will be created displaying the number of patients (and percentage) experiencing a treatment-emergent adverse event (TEAE) and the number of TEAEs for: any TEAE, any mild/moderate/severe TEAE, any unrelated/related TEAE, any serious AE, any serious TEAE, and any TEAE leading to study treatment discontinuation, any AE leading to death.

All TEAEs and those leading to death will be tabulated. SUSARs will be reported by the pharmacovigilance vendor.

All TEAEs are tabulated by System Organ Class (SOC) and Preferred Terms (PTs) within each SOC according to the MedDRA terminology list. TEAEs will be tabulated using frequency counts (number of patients with at least one event, and number of events) and percentage of patients with the event. Similar tables will be created for TEAEs leading to premature treatment discontinuation and Serious TEAEs. These summary tables will be presented by decreasing frequency of occurrence based on SOC and PT.

For summary tables, an AE is considered related if the causality to the study medication is classified as either ‘Probably Related’ or ‘Possibly Related’, where a missing relationship is also considered related. Otherwise, it will be considered unrelated for summary tables.

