## **5.7 Scheduled visits, dosing and treatment compliance**

Not applicable / not in the scope of this SAP following early termination of the study.

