### 9.3 End-of-text tables and graphs

Following ICH E3 guidelines, all tables and graphs mentioned here will be presented in Section 14 of the CSR, and tables will be prepared in the order and with section number as stated.

Table /graph number	Contents of table/graph
14.1 Demographic Data Summary figures and tables	
14.1.1	Demographics
14.1.2	Baseline Characteristics
14.1.3	ALS-specific history
14.1.4	Disposition
14.2 Efficacy Data Summary Figures and Tables	
14.2.1.1	Survival time: descriptive statistics
14.2.1.2	Survival time: Kaplan-Meier curves
14.2.1.3	Survival time: statistical analysis results (RMST)
14.2.2.1	Overall survival: descriptive statistics
14.2.2.2	Overall survival: Kaplan-Meier curves

14.2.2.3	Overall survival: statistical analysis results (RMST)
14.2.3.1	Descriptive statistics for absolute values and change from baseline ALSFRS-R total score and function domains
14.3 Safety Data Summary figures and tables – 14.3.1 Displays of Adverse Events	
14.3.1.1	Overview adverse events
14.3.1.2	Treatment emergent adverse events by SOC and PT
14.3.1.3	Treatment emergent serious adverse events by SOC and PT
14.3.1.4	Treatment emergent adverse events leading to treatment discontinuation by SOC and PT
14.3 Safety Data Summary figures and tables – 14.3.2 Listings of Deaths, Other Serious and Significant Adverse Events	
14.3.2.1	Deaths
14.3.2.2	TEAEs

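### The SAP omits the exposure and drug-stop tables promised in Protocol 11.3.5, so the primary TEAE percentages are reported without treatment duration or patient-years

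*Protocol*

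**What the plan says.** Protocol 11.3.5 (Safety Analysis), repeated in the statistical methods of the synopsis, states: "Exposure to study drug and reasons for discontinuation of study drug will be tabulated".

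The SAP section headed "Scheduled visits, dosing and treatment compliance" (5.7) reads in full: "Not applicable / not in the scope of this SAP following early termination of the study". SAP 5.6.2, on other safety endpoints, is closed in the same way. The table list in SAP 9.3 has four adverse event tables (14.3.1.1 to 14.3.1.4), none of them on exposure.

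For the primary endpoint, SAP 5.6.1 says: "A treatment emergent adverse event (TEAE) is defined as an adverse event that appears at or after first dosing of extension". The window has no end relative to the last dose. Results are numbers of patients, numbers of events and percentages. SAP 5.1 fixes the base of the percentages: "The denominator when calculating percentages will be the number of patients in the applicable analysis population". For safety that is SAFe, meaning everyone who took at least one extension dose. SAP 3.1.2 adds that "data will be presented also using the randomization groups of ADORE study".

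Two pieces of information on discontinuation remain. Disposition (SAP 5.4.3) covers "completed extensions along with reasons for early discontinuation. Completion status will be derived from CRF form", the form being the one for study completion. Table 14.3.1.4 is "Treatment emergent adverse events leading to treatment discontinuation by SOC and PT".

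**The concern.** A percentage of patients with an event depends on how long they were observed. Without treatment duration or patient-years, a reader of the report cannot tell how long-term the safety evidence is, cannot turn a percentage into a rate, and cannot compare it with another study of different length. Nor can the reader check whether the two ADORE arms, shown side by side, had similar time on FAB122 in the extension.

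Early termination is the only reason given for the reduced scope. It supports keeping the table. The synopsis planned about 3 years of study, and once that no longer holds, actual exposure cannot be inferred from the protocol.

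A second gap is smaller. Protocol 6.5 lets a patient stop FAB122 and stay in the study. Some of its listed reasons for stopping need not be adverse events, such as key safety assessments that cannot be done, pregnancy, or the investigator's view of the patient's interest. No planned table separates such patients.

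**Working it through.** **Step 1: commitment against planned output**

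| Item | Protocol | SAP |
|---|---|---|
| Exposure to study drug | Promised in 11.3.5 and the synopsis | Out of scope in 5.7; no table in 9.3 |
| Drug stops caused by a TEAE | Covered by 11.3.5 | Kept: count in 5.6.1, Table 14.3.1.4 |
| Drug stops for other reasons, patient stays in study | Covered by 11.3.5 | No table; disposition (14.1.4) takes its status from the study completion form |
| Leaving the study, with reasons | Promised in 11.3.3 | Kept: 5.4.3, Table 14.1.4 |
| Person-time behind TEAE percentages | Not promised separately | None; denominator is all SAFe patients |

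SAP Section 6 says that some protocol analyses are dropped, but does not name exposure or reasons for stopping drug.

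**Step 2: plausible range of duration**

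The documents state no TEAE rate, exposure or sample size calculation, so there is no figure to reproduce. Protocol 1.0 is dated 17 Oct 2022 and the SAP 19 Apr 2024. That is 550 days, and 550/365.25 = 1.51 years. It is an upper limit on extension follow-up if follow-up closed by the SAP date, which is an assumption. From the latest protocol date listed in SAP Section 1 (10 Jul 2023) to the SAP is 284 days, or 0.78 years. Entry was staggered, so individual durations could lie well below the upper limit.

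**Step 3: same rate, different percentage (assumed rates)**

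With a constant first-event rate r per patient-year and T years of follow-up, the percentage with the event is 100 × (1 − exp(−rT)).

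- r = 0.1: 4.9% at 0.5 years, 9.5% at 1 year, 13.9% at 1.5 years. The ratio of 1.5 to 0.5 years is 2.86.
- r = 0.5: 22.1%, 39.3% and 52.8%. The ratio is 2.39.

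A rate per patient-year would be the same at each duration.

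**Step 4: what zero events would show (assumed mean durations)**

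N = 200 to 225 is the anticipated enrolment in Protocol 11.2 and SAP 2.4. The one-sided 95% upper bound per patient is 1 − 0.05^(1/N), which is 1.49% for 200 and 1.32% for 225, whatever the follow-up. The bound on the rate is −ln(0.05)/(N × T), with −ln(0.05) = 2.996.

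- T = 0.25 years: 2.996/50 = 5.99 per 100 patient-years for N = 200; 2.996/56.25 = 5.33 for N = 225.
- T = 1 year: 1.50 and 1.33.
- T = 1.5 years: 1.00 and 0.89.
- T = 3 years (the planned period): 0.50 and 0.44.

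The same table of zeros rules out a rate of about 6 or about 1 per 100 patient-years, depending on a duration that the SAP does not report.

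**Step 5: the off-drug question**

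Protocol 6.5 allows regular follow-up after stopping drug. Protocol 6.4 offers phone contact for vital status to patients not willing to continue treatment. Footnote 5 of Table 1 limits those not taking the drug to phone contact, with no other assessments, and footnote 4 places the end-of-trial visit at discontinuation. Under the first text, AEs after stopping enter the TEAE count. Under the others, many stoppers would have no scheduled AE collection. The share of off-drug TEAEs cannot be derived from this, so none is estimated.

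**The case against.** The reduced scope is disclosed. SAP 2.1, 4 and 6 say that analyses were cut because of early termination, and the heading of 5.7 covers dosing. A reader might infer a silent omission, and the documents do not support that. What stands is that Section 6 does not name these tables.

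A reader might also infer that patients who stopped FAB122 cannot be identified. That is too strong. TEAE-caused stops are counted and tabulated, study-level reasons are in disposition, and the CRF is not among the documents, so it is not shown that drug-stop data are missing. Listings offer no clear help either way: SAP 9.3 names deaths and TEAEs under a listings heading, while 9.4 puts listings out of scope.

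A third tempting reading is that a sizeable share of TEAEs arose off drug. With no stopping data, and with Protocol 6.5 at odds with 6.4 and the Table 1 footnotes, no figure is defensible. The open TEAE window is also not an error, because it agrees with Protocol 9.1.1.

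Some time information survives. ALSFRS-R is summarised by group with patient numbers at each visit, and visits are every 3 months, so a rough retention profile by arm can be read off. But that profile measures attendance, and ALSFRS-R may be collected by telephone and, under 6.5, off drug. It does not give time on FAB122.

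Finally, events per 100 patient-years were never promised. That is correct: this part is a recommendation. The exposure table and the drug-stop table are commitments.

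**Conclusion.** The point holds as a gap between protocol and SAP that bears on the primary endpoint. Two promised tables are missing: exposure entirely, and reasons for stopping drug except for TEAE-caused stops. As planned, the TEAE results can describe which events occurred and in how many patients, but cannot say over how much treatment.

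The size is illustrative only. Under constant assumed rates of 0.1 to 0.5 per patient-year, the same risk gives percentages that differ 2.4- to 2.9-fold between 6 and 18 months, and 18 months is about the longest follow-up the document dates allow. The zero-event bound moves about sixfold between mean durations of 0.25 and 1.5 years. That duration matters is certain; what it was in this study is unknown.

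Patients who stop for non-AE reasons and remain in follow-up are not separated in any planned table. How many there are cannot be told from the documents. The omission should be corrected because it concerns the stated primary objective and is cheap to repair. It does not invalidate the TEAE counts themselves.

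**What to change.** Add two tables to SAP 9.3, by ADORE arm and overall:

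- Extension exposure: duration from first to last dose, and total patient-years.
- Study drug discontinuation: number of patients who stopped FAB122 and all reasons, including those who stayed in the study.

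Add events per 100 patient-years to the TEAE overview (14.3.1.1), keeping the planned counts and percentages. Optionally, flag TEAEs with onset after the last dose.

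First-dose date is already used in SAP 5.2. The documents do not show a last-dose field in the CRF. If there is none, approximate it from the sachet counts of Protocol 7.1.2 and the dated dispensing records of 7.1.3, and state the rule. These records may be held at sites outside the eCRF, which should be checked first.

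If exposure stays out of scope, name it in SAP Section 6 and state in the report that TEAE percentages have no treatment duration behind them.

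The cost is a small amount of programming and, where last dose is approximated, some imprecision in exposure. SAP Section 1 foresees new versions and finalization before database lock. After lock, the tables can be issued as a labelled addendum.

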#### **11.3.5.1. Physical Examination**

All abnormalities reported by the physical examinations will be listed and tabulated by treatment arm. Weight (kilograms), Height, and BMI (calculated) will be summarized by treatment and time.

#### **11.3.5.2. Adverse Events**

All treatment emergent AEs (TEAE) will be coded using the Medical Dictionary for Regulatory Activities (MedDRA version 23.0) coding dictionary. And all preferred terms (PT) will be tabulated by System organ Class (SOC) and additional tabulations will be made by severity and drug relatedness. A separate table (or listing will be created for serious TEAEs (SAE).

#### **11.3.5.3. Concomitant Medication**

All concomitant medications will be summarized by medication class or ATC classification.

#### **11.3.5.4. Laboratory Parameters**

Clinical laboratory tests (including re-check values if present) will be listed chronologically. 'H' and 'L', denoting values above or below the investigator reference range (when present), will flag out-of-range results. At each time point, absolute values and change from baseline of the hematology and chemistry variables will be summarized by treatment and time with n, mean, SD, SEM, median, Min, and Max values. The categorical data of the urinalysis will be summarized by treatment and time in frequency tables by variable.

#### **11.3.5.5. ECG**

From the 12-lead ECG data, HR, PR, RR, QRS, QT, and QTcF will be reported for each time-point and summarized using descriptive statistics. Mean (SD) temporal profiles for 12-lead ECG (QT, QTcF) will be presented graphically. The frequency (number) of clinically significant findings may be reported and summarized.

#### 11.3.5.6. Vital Signs

Vital signs, including blood pressure, pulse rate, respiratory rate, pulse oximetry and temperature will be summarized at each time point, using descriptive statistics and will be presented graphically.

---

## 12. DATA MANAGEMENT

### 12.1. Case Report Form

The investigator or designee will record all data collected in the eCRF provided for that purpose. The site will be suitably trained on the use of the eCRF and appropriate site personnel will be provided electronic signatures.

Completed eCRFs will be submitted according to the instructions of the CRO and reviewed by the CRO to determine their acceptability. If necessary, data correction requests will be generated for resolution by the study site. The investigator or designee will make necessary eCRF corrections.

All site entries will be made in a secured web site and the Principal Investigator (PI) will review the record for completeness. Upon completion of the review, including review of any corrections, the PI will sign electronically in the signature page of the eCRF.

### 12.2. Source Data

Patient confidentiality is strictly held in trust by the participating investigators, research staff, and the Sponsoring institution and their agents. This confidentiality is extended to cover testing of biological samples and genetic tests in addition to the clinical information relating to patients. Authorized representatives of the Sponsoring institution, Ethics Committee and Regulatory Authorities may inspect all documents and records required to be maintained by the investigator, including but not limited to, medical records (office, clinic or hospital) and pharmacy records for the patients in this study. The clinical study site will permit access to such records. Any data, specimens, forms, reports, and other records that leave the site will be identified only by a patient identification number to maintain confidentiality.

The investigator must maintain adequate and accurate records to enable the conduct of the study to be fully documented and the study data to be subsequently verified. These documents include Investigators' Study Files and original patient clinical source documents generated at the study site. The term "original" means the first recording of the data.

The investigator will ensure the site master files are maintained, including the study protocol and its amendments, IRB/IEC and regulatory approvals with associated correspondence, informed consents, study drug records, staff curriculum vitae, all correspondence, and other appropriate documents.

Patient clinical source documents may include, but are not limited to, patient hospital/clinic records, physicians' and nurses' notes, appointment books, laboratory reports, ECGs, radiographs, pathology and special assessment reports, and consultant letters. The investigator must assure that all original source documents are available to support monitoring activities.

